7.8 Treatment control

Medication dispensation

At the pharmacy service of each hospital sufficient pazopanib tablets are to be dispensed to patients in order to complete 4-week treatment periods.

Treatment fulfilment

In the medical diary of the patient the total number of pazopanib tablets taken and returned by the patient must be written. This information is to be entered in the e-CRF.

7.9 Biological sample collection

Tumor block collection

A paraffin-embedded block will be collected during the screening period for central pathological review. First diagnosis sample or another more recent available sample obtained during the routine care previous to study entry will be acceptable. Tumor biopsy at study entry will not be compulsory but recommended if clinically acceptable (e.g. superficial or easily accessible locations). It is strongly recommended if the previous histological material of the patient stems from more than one year in cases with pauci-symptomatic disease or in any fast growth rate tumor, before enrollment. The main reason is that in some surgical series there were focal poorly differentiated areas (which could be absent in the shipped block) in cases that ultimately died after metastatic recurrence of the anaplastic component. A post-treatment tumor sample will be collected when possible (selected patients for whom post-treatment biopsy could be performed). Please see the translational research section for more details on tumor block collection.

Blood sample collection

Serum will be collected as described:

- Three 5-mL tubes within 72 hours prior to starting the treatment (baseline).
- Three 5-mL tubes within 72 hours after radiological response is documented.
- Three 5-mL tubes within 72 hours after progressive disease is documented.

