3.3 Translational objectives

SFT cohorts:

- To perform a central pathologic review (diagnosis confirmation) of paraffin-embedded tumor blocks for each recruited patient with SFT, including (exploratory) STAT6 immunohistochemistry.
- To evaluate the serum profile of serum cytokine markers as indicator of response to pazopanib. The Luminex technology will be employed for the analysis of 12 cytokines [VEGF-A, PlGF-1, SDF-1 alpha (CXCL12), TNF alpha, IL-8, IL-6, PDGF –beta, HGF, E-Selectine, ICAM1, MMP-9 and FGFb].
- To evaluate the profile of angiogenic markers in the primary tumor and/or in the subsequent biopsies. Microvessel density (MVD) and VEGF/PDGF pathways will be evaluated by IHQ expression as well as their correlation with prognosis and their role as predictive factors to treatment with pazopanib (response, PFS and OS).
- To evaluate pharmacodynamic markers (MVD, VEGF/PDGF) only in patients with paired samples (in the biopsies taken after treatment).

EMC cohort:

- To perform a central pathologic review (diagnosis confirmation) of paraffin-embedded tumor blocks for each recruited patient with EMC, including FISH analysis and/or RT-PCR NR4A3 and its partners (EWSR1, TAF15).
- To evaluate the expression and activation profile of angiogenic targets (VEGFR, PDGFR, RET, MCSR1) in the primary tumor and/or in the subsequent biopsies by immunohistochemistry, pRTK array and IP/WB respectively.

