- (6) Physical examination every 4 weeks until 6 months of treatment and every 8 weeks after 6 months of treatment.
- (7) Monitoring of BP only: A measurement of BP should be taken at day 8+/-3 days. BP can be assessed by any method (i.e. at home or by another physician) as long as the study physician is informed of the measurement, verifies any measurement that is not normal and takes appropriate action.
- (8) ECG: Every 4 weeks until 6 months of treatment. Every 8 weeks after 6 months, until end of treatment.
- (9) Tumor sample will be collected before treatment.
- (10) Selected patients for whom post-treatment biopsy could be performed.
- (11) Serum will be collected as described:
 - Within 72 hours prior to starting treatment (baseline).
 - Within 72 hours after radiological response is documented.
 - Within 72 hours after progressive disease is documented.

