12.3 Biological sample collection

The samples to be collected for both SFT and EMC patients are:

1. One representative paraffin-embedded tumor block of the diagnostic biopsy/resection (mandatory) taken at pre-treatment stage (screening).
2. Three 5-mL tubes of peripheral blood within 72 hours prior to starting treatment (baseline).
3. One representative paraffin-embedded tumor block (selected patients for whom post-treatment biopsy could be performed).
4. Three 5-mL tubes of peripheral blood within 72 hours after radiological response is documented.
5. Three 5-mL tubes of peripheral blood at the end of treatment (within 72 hours after progressive disease is documented).

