12.4 Translational analytical methods

In the case of serum, the kinetic profile of each biomarker will be considered (increased, constant, decreased). All parameters analyzed will be correlated with progression-free survival (PFS), objective tumor response, overall survival (OS) and histopathological parameters.

For the statistical analysis, binary variables will be used, which will reflect the positivity status of measurements (yes/no; presence; absence).

The association with histopathological parameters and objective tumor response, all categorical, will be calculated through chi-squared test in order to determine the homogeneity or lineal tendency for the ordinary variables.

The statistical significance level will be of 5%. With the aim of studying the impact of histology, immunohistochemistry and molecular factors on PFS and OS, the proportional method Kaplan-Meier (log rank) will be used. The evidence of relative risk for each patient will be provided by means of a Cox proportional hazards model, by using a stepwise selection to identify the independent predictors of poor outcome.

Multivariate analysis will be performed for the biomarker study if the number of cases available for the study is at least 10-fold the number of variables involved. Otherwise, standard univariate pre and post tests will be used.

For the shipment of biological samples, please contact:

Sofpromed Investigación Clínica, SLU
[name], [name]
[name], [name]
[contact]
[contact]
[contact]
E-mail: [contact]

An additional document will be provided in the Investigator Site File with detailed guidelines regarding biological sample management.

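### All post-baseline serum draws are triggered by response or progression, so the cytokine change class is confounded with the outcomes it is to be correlated with

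*Protocol*

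**What the plan says.** Protocol section 7.9 lists three serum draws. Only the first has a time that does not depend on outcome: "Three 5-mL tubes within 72 hours prior to starting the treatment (baseline"). The second is taken in responders alone, and its trigger reads: "Three 5-mL tubes within 72 hours after radiological response is documented". The third waits for the disease to worsen, and no calendar week is attached to it either.

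Footnote 11 to Table 5 (section 7.1) repeats the schedule, including "Within 72 hours after radiological response is documented". Section 12.3 does too, and ties the last draw to progression: "Three 5-mL tubes of peripheral blood at the end of treatment (within 72 hours after progressive disease is documented"). None of the three places gives a serum draw at a fixed week on treatment.

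The SFT objective in section 3.3, repeated in 12.2, is "To evaluate the serum profile of serum cytokine markers as indicator of response to pazopanib", using 12 cytokines. Section 12.4 sets the analysis variable: "the kinetic profile of each biomarker will be considered (increased, constant, decreased"). On the outcomes to be studied, the same section says: "All parameters analyzed will be correlated with progression-free survival (PFS), objective tumor response, overall survival (OS) and histopathological parameters". The tests named there are chi-squared for categorical outcomes, and Kaplan-Meier with log-rank and Cox regression for PFS and OS, at a 5% level.

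**The concern.** A class of increased, constant or decreased needs a second sample. Under this schedule the second sample exists only because the patient has responded or progressed. If responders are classed on blood drawn at response and never-responders on blood drawn at progression, the comparison sets one disease state against another, usually at different times on drug. A cytokine that only follows current tumour state could then be reported as an indicator of response.

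The survival analyses have a related problem. The class is not known at treatment start. It becomes known at response, which requires having stayed progression-free until then, or at progression, which is the PFS event itself.

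An analysis plan cannot repair this later, because on-treatment samples that were never drawn cannot be analysed.

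**Working it through.** **Plan's own figure.** The protocol gives no sample size, power or error rate for the serum analysis, so there is nothing to reproduce. The check compares the schedule with the analysis and then sizes the effect by illustration.

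**Step 1: which changes can be computed** (sections 7.1, 7.9, 12.3)

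| Patient | Scheduled serum | Change available |
|---|---|---|
| Responds, later progresses | baseline, response, progression | to response and to progression |
| Responds, not progressed | baseline, response | to response only |
| Never responds, progresses | baseline, progression | to progression only |
| Never responds, no documented progression | baseline | possibly none |

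No change measure is available in all patients, and none is taken at a common time. A baseline-to-response change exists only in responders. A baseline-to-progression change exists only in patients who have had the PFS event.

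**Step 2: how many patients.** The maximum SFT sample is 30 + 31 = 61 (section 1). The design response rates are 0.40 and 0.60 (section 11.3). Never-responders, who have no scheduled on-treatment serum before progression:

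- at 60% response: 61 × (1 − 0.60) = 24.4, about 24
- at 40% response: 61 × (1 − 0.40) = 36.6, about 37

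If stratum 1-b stops after its first stage of 23, the total is 30 + 23 = 53, and the same formula gives 53 × 0.40 = 21.2 to 53 × 0.60 = 31.8.

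**Step 3: PFS and OS.** OS runs from treatment start (section 11.2); the same origin is assumed here for PFS. A patient classed at the response draw cannot, by construction, have progressed or died before that draw. Counting that interval as follow-up in the class is immortal time. A patient classed at the progression draw is classed at the PFS event, so the class cannot precede the outcome.

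**Step 4: illustration for response.** These assumptions are not in the protocol:

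- 61 patients, 50% response, 3,000 simulated trials;
- change score with SD 1, cut at ±0.5 SD into three classes;
- a marker with no predictive value for response;
- each patient classed on the first post-baseline draw, with every non-responder having a progression draw;
- response draw at week 8 or 16; progression times exponential with mean 26 weeks, moved up to the next 8-weekly scan.

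The test is chi-squared of class against response at 5%. In the disease-state scenario the mean change is minus the shift at response and plus the shift at progression. In the drift scenario the mean change is proportional to weeks on drug at the draw. The comparator is one draw at week 4 in everyone, with the same drift.

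| Size (SD; for drift, SD per 26 weeks) | Disease-state shift | Drift with time | Common draw |
|---|---|---|---|
| 0 | 4.7% | 5.3% | 4.8% |
| 0.25 | 31% | 6.7% | 5.0% |
| 0.5 | 86% | 14% | 5.1% |
| 0.75 | 99.7% | 20% | 5.1% |
| 1 | 100% | 23% | 5.3% |

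With event-triggered draws the false-association rate exceeds 5% in both scenarios, modestly for drift and severely for disease-state shifts. With a common draw it stays at about 5%.

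**The case against.** Several points on the other side stand.

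- **Responders who later progress also give a progression draw.** Section 12.4 does not say which later sample defines the class, so comparing response draws with progression draws is one reading. A baseline-to-progression change in both groups would remove the disease-state contrast. It would still be limited to patients who have progressed, at times set by PFS.
- **The objective speaks of an indicator.** An indicator may be concurrent, and event-triggered samples can describe marker levels at response and at progression.
- **Kaplan-Meier and log-rank are named for histology, immunohistochemistry and molecular factors.** Serum change is brought in only by the general sentence about correlating all parameters. Landmark handling could be left to an analysis plan, but a landmark analysis of change still needs a sample taken by the landmark.
- **Table 5 marks blood collection under end of treatment.** Some patients stopping for other reasons may therefore be sampled, although section 12.3 ties that draw to progression.

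A reader might infer that the analysis is circular and the serum objective unanswerable. The documents do not support that. The outcome fixes the timing and existence of the draw, not the direction of change, and baseline levels precede every outcome.

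A reader might also infer near-certain false findings. For example, a 1 SD rise at progression in everyone, with 30 responders against 30 non-responders and a change SD of 1, gives z = 1 × √(30 × 30/60) = 3.87 and a detection probability of Φ(3.87 − 1.96) = 0.97. That figure needs the response-versus-progression reading and an assumed shift. If progression draws are compared in both groups, the difference vanishes. Nor will every marker that changes with time on drug mislead: the drift rates above are only 7-23%.

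**Conclusion.** The concern holds for the change-from-baseline analysis. No common on-treatment sample exists, and about 24 to 37 of at most 61 SFT patients have no scheduled serum between baseline and progression. Correlating the change class with response is confounded by disease state and time at the draw. Correlating it with PFS or OS from treatment start carries immortal-time bias.

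The counts rest on the protocol's own response rates and maximum enrolment. The false-association rates (about 7-23% for drift of 0.25-1 SD per 26 weeks, 31-99.7% for disease-state shifts of 0.25-0.75 SD) rest on the assumptions listed and show a range, not a prediction. Baseline cytokine levels can still be related to response, PFS and OS. The problem is confined to one translational objective and does not touch the primary endpoint.

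**What to change.** In sections 7.9 and 12.3 and in Table 5 footnote 11, add one serum draw at a common early on-treatment visit where blood is already taken. It should fall at or before the first scheduled imaging (about week 8), in all patients still on treatment. A draw before that scan has the advantage that no scheduled scan has yet been read. Keep the response and progression draws and label them descriptive.

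In section 12.4, define the change class from baseline to the common draw only, and relate it to PFS and OS counted from that landmark.

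If no draw can be added, limit inferential tests against response, PFS and OS to baseline levels, and report event-triggered changes descriptively. This needs only a change to section 12.4.

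The cost of the preferred option is a protocol amendment, some extra tubes and some extra Luminex assays. Patients who progress or die before the landmark drop out of the landmark analysis.

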7.10 Survival

All patients should be followed until death, if possible. The date and cause of death must be evaluated and documented in the e-CRF. Follow up visits should take place every 12 weeks after tumor progression. In these visits patient status will be assessed (alive, dead, lost to follow up), as well as any new anti-cancer treatments.

8. PHARMACOVIGILANCE

ICH GCP requires that both investigators and sponsors follow specific procedures when reporting adverse events/reactions in clinical trials. Any event involving adverse drug reactions, illnesses with onset during the study or exacerbations of pre-existing illnesses should be recorded. In addition, clinically significant changes in physical examination findings and abnormal objective test findings (e.g. ECG) should also be recorded as adverse events. The criteria for determining whether an abnormal objective test finding should be reported as an adverse event are as follows:

- test result is associated with clinically significant symptoms, and/or
- test result leads to a change in study dosing or discontinuation from the study, significant additional concomitant drug treatment or other therapy, and/or
- test result leads to any of the outcomes included in the definition of a serious adverse event, and/or
- test result is considered to be an adverse event by the investigator.

8.1 Definitions

Adverse Event (AE)

Any untoward medical occurrence in a patient or clinical investigation subject which does not necessarily have a causal relationship with the study treatment.

Adverse Reaction (AR)

All untoward and unintended responses to an investigational medicinal product related to any dose administered.

Serious Adverse Event (SAE) / Serious Adverse Reaction (SAR)

Any untoward medical occurrence or effect that at any dose:

- results in death (is fatal),
- is life-threatening,
- requires or prolongs inpatient hospitalization,
- results in persistent or significant disability or incapacity,
- is a congenital anomaly or birth defect, or
- is medically significant.

Medical and scientific judgment should be exercised in deciding whether urgent reporting is appropriate in other situations such as important medical events that may not be immediately life-threatening or result in hospitalization but may jeopardize the patient or may require intervention to prevent one of the outcomes listed in the above definition.

Any suspected transmission of an infectious agent through the medication is also considered a SAE. Additionally, all hepatotoxicities as defined below are also considered SAEs for the purposes of this clinical trial:

- ALT > 3.0 x ULN with concomitant elevation in bilirubin (defined as total bilirubin \geq 2.0 x ULN, with direct bilirubin > 35%) or with hypersensitivity symptoms (e.g. fever, rash) —bilirubin fractionation should be performed if testing available.
- ALT > 8.0 x ULN without bilirubin elevation (defined as total bilirubin < 2.0 x ULN or direct bilirubin \leq 35%) and without hypersensitivity symptoms (e.g. fever, rash) —bilirubin fractionation should be performed if testing available.

Suspected Unexpected Serious Adverse Reaction (SUSAR)

A SUSAR is a SAR that is classified as 'unexpected' (i.e. a serious adverse reaction), the nature and severity of which is not consistent with the information about the medicinal product in question set out in the summary of product characteristics for that product.

The last version of Summary of Product Characteristic available in EMEA website will be the reference document to establish the AE expectedness for pazopanib.

Life Threatening Event

It is any event in which the subject was at risk of death at the time of the event; it does not refer to an event which hypothetically might have caused death if it were more severe.

Hospitalization / Prolongation of Hospitalization

Any event requiring hospitalization (or prolongation of hospitalization) that occurs or worsens during the course of a patient's participation in a clinical study must be reported as a serious adverse event. Prolongation of hospitalization is defined as any extension of an inpatient hospitalization beyond the stay anticipated/required for the initial admission, as determined by the investigator or treating physician.

Hospitalizations that do not meet criteria for serious adverse event reporting are:

- a) Reasons described in protocol (e.g., drug administration, protocol-required investigations). Hospitalizations or prolonged hospitalization for a complication of therapy administration or procedures will be reported as Serious Adverse Event.
- b) Hospitalization or prolonged hospitalization for technical, practical or social reasons, in absence of an adverse event.
- c) Pre-planned hospitalizations (i.e., planned before study entry). Any surgery or procedure planned before study entry must be documented on the case report form.

Unexpected Adverse Reaction

An unexpected adverse reaction, the nature or severity of which is not consistent with the applicable product information.

The last version of Summary of Product Characteristic available in EMEA website will be the reference document to establish the AE expectedness for pazopanib.

AE Associated with the Use of the Drug

An adverse event is considered associated with the use of the drug if the causality assessment is related to study drug or is unknown according to definitions listed below.

Causality Assessment

The investigator must provide an assessment of causality of the study drug according to the following criteria:

- **Yes.** There is a reasonable chance that the study drug caused the SAE.
- **No.** There is not a reasonable chance that the study drug caused the SAE and other causes are more likely.
- **Unknown.** It should only be used in special situations where the investigator has insufficient information (e.g. the patient was not attended in his/her center) and when none of the above options can be utilized.

8.2 Adverse event reporting

The Sponsor (through the appointed CRO in charge of pharmacovigilance) will collect AEs up to 30 days after administration of the last dose of study drug. All adverse events must be recorded using medical terminology in the source document and the electronic CRF. Investigators must assess the severity (grade) of the event

following NCI-CTCAE 4.0 criteria and assign a relationship to study therapy and pursue and obtain information adequate both to determine the outcome and to assess whether it meets the criteria for classification as a SAE requiring immediate notification. The investigator must provide any information as requested by the Sponsor in addition to that collected on the e-CRF.

Any serious adverse events which occur from patient informed consent signature, during the clinical study or within 30 days of receiving the last dose of study medication, whether or not related to the study drug, must be reported by the investigator. In addition, any SAEs which occur as a result of protocol-specific diagnostic procedures or interventions must also be reported. Beyond this period of time, only those SAEs suspected to be related to the study drug will be reported.

All SAEs suspected to be related to study treatment should be followed after the treatment/study withdrawal until the event or its symptoms have resolved or stabilized at a grade acceptable to the investigator, coordinating investigator and/or Sponsor.

Site investigation staff should notify the Sponsor (via the appointed CRO) all the pregnancies of female subjects that occurred during the clinical trial within 24 hours from becoming aware. Site investigation staff, should also communicate the outcome of the pregnancy within 24 hours since the awareness.

The cause of death of a deceased patient in a clinical trial, whether the case of an expected event or associated with the investigational agent, is considered an SAE and therefore must be communicated using the SAE form. The autopsy report should be sent to Sponsor identified only with the patient trial number.

Additionally, all hepatotoxicities as defined below are also considered SAEs for the purposes of this clinical trial:

- ALT > 3.0 x ULN with concomitant elevation in bilirubin (defined as total bilirubin \geq 2.0 x ULN, with direct bilirubin > 35%) or with hypersensitivity symptoms (e.g. fever, rash) —bilirubin fractionation should be performed if testing available.
- ALT > 8.0 x ULN without bilirubin elevation (defined as total bilirubin < 2.0 x ULN or direct bilirubin \leq 35%) and without hypersensitivity symptoms (e.g. fever, rash) —bilirubin fractionation should be performed if testing available.

All SAEs and SUSARs, taking place in any country, must be directly communicated by fax or email within 24 hours to the study CRO in Spain:

Sofpromed Investigación Clínica, SLU
[contact]
[contact]
[contact]
E-mail: [contact]

The SAE report should comprise a full written summary, detailing relevant aspects of the adverse events in question. Where applicable, information from relevant hospital case records and autopsy reports should be included. Follow-up information should be forwarded to the study CRO in Spain within 24 hours.

All SAEs suspected to be related to study drug must be followed up after the time of therapy discontinuation until the event or its consequences resolve or stabilize at an acceptable level for the investigator, the coordinating investigator and/or Sponsor.

